| Title | A Study to Evaluate the Performance, Usability, and Reliability of a Novel System for Continuous Collection of Physiological Data in Healthcare and Remote Settings |
| Investigational Device | BioStamp nPoint™ |
| Indications for Use | 
The BioStamp nPoint system is a wireless remote monitoring system intended for use by researchers and healthcare professionals for continuous collection of physiological data in home and healthcare settings. These physiological data include heart rate, heart rate variability, respiration rate, activity (including step count and activity classification), and posture (body position relative to gravity). The system is also intended for measurement of surface electromyography and to monitor limb or body movements during daily living and sleep. Data are transmitted wirelessly from the Sensors for storage and analysis.
 
The device is intended for use on general care patients who are 18 years of age or older as a general patient monitor to provide physiological information. The data from the BioStamp nPoint system are intended for use by researchers and healthcare professionals for research applications or, at the discretion of a qualified healthcare professional, as an aid to diagnosis and treatment. The device is not intended for use on critical care patients.
 |
| Study Type | Interventional |
| Study Phase | Pivotal study for FDA 510(k) submission |
| Study Objective | 
The primary objective of the clinical investigation is to:
 
 Evaluate the accuracy of BioStamp nPoint system algorithm measurements and to evaluate the adhesion (reliability) of BioStamp nPoint Sensors. |
| Study Design | A single-site, non-significant risk, open-label, prospective non-randomized clinical investigation designed to validate the accuracy of the various physiological parameters that the Wearable Sensor Patches acquire and the system processes as well as to validate the performance of the skin adhesive |
| Enrollment Size | Twenty-five (25) subjects minimally will be enrolled in the study. |
| Number of Sites | One site in the United States. |
| Subject Population | Healthy adult subjects will be recruited to participate in this study. |
| Effectiveness Endpoints | 
The effectiveness endpoints for this study are the various types of measurements made by the BioStamp nPoint system. All effectiveness endpoints to be statistically summarized will be collected using the BioStamp nPoint and are as follows:
 
 Heart Rate (bpm) Heart Rate Variability (RMSSD¹ (msec) and LF/HF Ratio²) |

¹ RMSSD: root-mean-square of successive difference of the time intervals between successive heartbeats.

| | 
 • Respiration (average respiration rate) • Activity Classification (activities – sleep, standing, sitting, lying, walking and other) • Activity Parameters - total step counts in a 6 minute walk test • Sleep (sleep onset time (hours, minutes, and seconds), sleep wake time (hours, minutes, and seconds)) • Posture Classification (sleep posture, stationary posture standing, stationary posture sitting) 
For each endpoint, the BioStamp nPoint measurements will be compared to a similar FDA approved measurement device, other simplistic measurement devices, or to independent observer measurements. The FDA approved measurement devices for this study are the Actiheart heart rate reference device and the Capnostream™ portable respiratory monitor.
 
  
 Endpoint Variable Group	Measurement Comparator	
   
 Heart Rate	Actiheart Device	
 
 Heart Rate Variability	Actiheart Device	
 
 Respiration	Capnostream Device	
 
 Activity Classification	Independent Observer	
 
 Activity Parameters	Manual Step Counting Device	
 
 Sleep Parameters	Independent Observer	
 
 Posture	Independent Observer	
  
 | Endpoint Variable Group | Measurement Comparator | Heart Rate | Actiheart Device | Heart Rate Variability | Actiheart Device | Respiration | Capnostream Device | Activity Classification | Independent Observer | Activity Parameters | Manual Step Counting Device | Sleep Parameters | Independent Observer | Posture | Independent Observer |
|---------------------------|---|-------------------------|------------------------|------------|------------------|------------------------|------------------|-------------|--------------------|-------------------------|----------------------|---------------------|-----------------------------|------------------|----------------------|---------|----------------------|
| Endpoint Variable Group | Measurement Comparator | | | | | | | | | | | | | | | | |
| Heart Rate | Actiheart Device | | | | | | | | | | | | | | | | |
| Heart Rate Variability | Actiheart Device | | | | | | | | | | | | | | | | |
| Respiration | Capnostream Device | | | | | | | | | | | | | | | | |
| Activity Classification | Independent Observer | | | | | | | | | | | | | | | | |
| Activity Parameters | Manual Step Counting Device | | | | | | | | | | | | | | | | |
| Sleep Parameters | Independent Observer | | | | | | | | | | | | | | | | |
| Posture | Independent Observer | | | | | | | | | | | | | | | | |
| Data Management | 
MC10 sensor and system data to be uploaded to the MC10 cloud by subject and clinical site. MC10 system and reference device to be returned to the clinical site by the subject after completion of protocol activities.
 
All clinical study source documents to be retained at the site. Copies, where applicable, to be provided to MC10. Reference device data to be downloaded on site and both retained on site and provided to MC10. Any external electronic storage (e.g. DVD) to be retained by the site as source documents.
 | | | | | | | | | | | | | | | | |
| Safety | 
All adverse events (AEs) reported during the evaluation period will be collected and summarized. Serious AEs (SAEs) will be reported in accordance with US Code of Federal Regulation requirements.
 | | | | | | | | | | | | | | | | |
| Inclusion Criteria | 
Subjects must meet all of the following criteria to be eligible for participation in the study:
 
Inclusion Criteria
 
 1. Male or female volunteers, at least 18 years of age at the time of screening visit; 2. Fluent in English; 3. The subject is willing to comply with the protocol specified evaluations; 4. Subject is willing and cognitively able to sign informed consent | | | | | | | | | | | | | | | | |
| Exclusion Criteria | 
Subjects must be excluded from participation in this study if any of the following criteria are met:
 
Exclusion Criteria
 
 1. Pregnancy; | | | | | | | | | | | | | | | | |

² LF/HF ratio: the ratio of power in the low-frequency (LF, 0.04-0.15 Hz) and high-frequency (HF, 0.15-0.4 Hz) bands of heart rate variability in the frequency domain.

| | |
|--|--|
| | 
 2. Positive urine drug screen 3. History of active (clinically significant) skin disorders; 4. History of allergic response to silicones or adhesives; 5. Subjects with electronic implants of any kind (e.g. pacemaker) 6. History of sleep disorders or self-reported insomnia or other sleep conditions; 7. Broken, damaged or irritated skin or rashes near the sensor application sites; 8. Subjects that are MC10 employees or shareholders, or a spouse or child of an MC10 employee or shareholder; 9. Subjects who are physically or cognitively unable to normally perform activities of daily living, assessed at the discretion of the investigator. |
| Remuneration | 
Subjects will receive \$50 for on-site screening that results in screen fail or enrollment, and a subsequent \$1050 for successfully completing the study, where completion is defined as completing the baseline clinic visit, wearing the sensors for two days, returning the sensors to the coordinators, and completing the usability survey.
 |
| Study Duration / Follow-up Period | 
A supervised session which includes one awake and two night-time sleep periods with observation periods throughout; thus a total evaluation duration of approximately 48 hours.
 
One safety and tolerability follow-up call will occur within three to five days post-sensor removal.
 |
| Data Analysis Plan | 
The following analysis populations will be defined for the study:
 
 • Intent-to-Measure (ITM) Population – The ITM population will consist of all subjects who are enrolled in the study and for which the ability of each measurement device to measure the subject has been established. • Safety Population – The safety population will consist of all subjects who are enrolled in the study. 
The ITM population will be the primary analysis set for all effectiveness analyses. The safety population will be used for the analysis of all safety variables and baseline characteristics.
 
For each effectiveness endpoint, the BioStamp nPoint measurements will be compared to the noted comparator device or to independent observer measurements.
 
For pairs of measurements collected on the continuous scale (quantitative to quantitative comparisons), scatter plots with the 45 degree line of agreement superimposed will be constructed from paired observations from the two sources (BioStamp nPoint vs comparator) along with Bland-Altman plots of the data. The mean absolute error (MAE) and the root-mean-square error (RMSE) estimates of agreement will be calculated for each comparison. The standard deviations of each of the agreement measures will also be computed.
 
For pairs of measurements collected on a categorical scale (qualitative to qualitative comparisons), two-way tables of agreement will be constructed for each comparison. The agreement percentage will be computed for each table.
 
The number and percentage of sensor patches in each category of the adhesion
 |

| | |
|-------------------------------|--|
| | scoring scale will be tabulated. |
| ClinicalTrials.gov | Sponsor responsible for study registration per 42 CFR Part 11. |
| Principal Investigator | [REDACTED] |
| Sponsor | MC10, Inc. [name] |
| Sponsor Contact | [REDACTED] MC10, Inc. [name] |

Table of Contents

| | |
|--|----|
| CONFIDENTIALITY STATEMENT | 1 |
| PROTOCOL SYNOPSIS | 4 |
| LIST OF ABBREVIATIONS | 12 |
| 1.0 BACKGROUND AND RATIONALE | 13 |
| 2.0 DEVICE DESCRIPTION | 13 |
| 2.1 Principles of Operation | 14 |
| 2.2 Indications for Use | 14 |
| 3.0 STUDY PURPOSE AND OBJECTIVES | 15 |
| 4.0 STUDY ENDPOINTS | 15 |
| 4.1 Effectiveness Endpoints | 15 |
| 4.2 Safety | 17 |
| 5.0 STUDY DEVICES | 17 |
| 6.0 STUDY DESIGN | 19 |

1.0 BACKGROUND AND RATIONALE

Objective and validated assessments of physiological metrics are critical for monitoring data and data trends, and as an aid to assessing disease progression and subsequent therapeutic intervention. In current clinical practice and medical product development, patient historical data, patient-reported outcomes, and in-clinic assessments by physicians are used to evaluate biometrics, but these evaluations are time and context limited and present an incomplete picture of the subject as well as his/her current condition. Some assessments are subjective, or rely on a patient's memory and perception. Other assessments are limited to a specific time interval in a particular environment, like a clinic, preventing accurate longitudinal assessment of fluctuations in physiological parameters. This is particularly true of measurements taken by large stationary clinical instruments, which may limit not only the setting for the measurement but may also affect the subject and change the outcome of the measurement itself.

Wearable sensors have the potential to enable longitudinal, objective monitoring of clinical signs across patient populations, but conventional wearable devices are typically comprised of rigid, packaged electronics, which may compromise overall subject comfort, are often plainly visible when worn in public, and can interfere with activities of daily living and sleep. Finally, emergence of smartphone and wrist-based sensing has led to potential improvements in access and ease of use, but themselves carry limitations in night-time sensing or in creating lower-extremity insight. Consequently, there is a need for assessment tools that are unobtrusive and provide clinical quality, medical grade continuous assessments from multiple body locations.

Conformal, body-worn sensors may provide an easy-to-use and objective alternative. Previously, studies have shown that wearable sensors can be used to provide greater insight into neurological (e.g. Parkinson's disease¹, Huntington's disease², multiple sclerosis³), sleep⁴ (e.g. periodic limb movements, respiration), cardiac monitoring⁵ and orthopedics (e.g. physical rehabilitation⁶) movement and biopotential measurements. These studies have demonstrated that data can be collected in an unobtrusive way in remote settings, supporting the possibility of providing more robust, data-based evidence to the clinician and thus to the patient.

The BioStamp nPoint system combines a traditional, electronic platform for collecting Patient Reported Outcomes with multiple, location-agnostic sensors in an adhesive bandage-like form factor. These sensors are flexible enough to conform to the human body and eliminate the profound mismatch in physical properties at the interface between conventional wearable devices and the human body. This new class of soft, conformal electronics and sensors interface better with the surface of the body to minimize discomfort and optimize skin coupling over prolonged use and multiple data-gathering locations. The potential for both in-clinic and remote, longitudinal, multi-sensor, multi-modal, passive and prescribed biometric data tracking is noteworthy.

This first clinical evaluation aims to evaluate the accuracy, reliability, and ease of use of the BioStamp nPoint system as well as the safety, fidelity and tolerability of the BioStamp nPoint Sensors.

2.0 DEVICE DESCRIPTION

The BioStamp nPoint system is a wireless remote monitoring platform intended for use by healthcare professionals and researchers for the continuous collection of physiological data in home and healthcare settings. The system is designed principally for data collection during research studies although may be used wherever and whenever collection of the relevant data is needed.

Figure 1: Illustration of BioStamp nPoint Sensor

The BioStamp nPoint system centers on body-worn Wearable Sensor Patches (“Sensors”, “WSPs”) which can be worn in both in clinic (“supervised”) and remote (“unsupervised”) settings for up to 24 hours at a time, and can be worn repeatedly for multiple days. Study facilitators (either researchers or physicians) set up data collection studies using a web-based study configuration tool, called the Web Portal. For in-clinic uses, the BioStamp nPoint system includes an Investigator Tablet Application that study facilitators use to connect to and configure Sensors. When used at home, study subjects interact with the system through a Mobile Phone Application, the Link App. The Link Hub is used to charge and synchronize data from the Sensors. The BioStamp nPoint system includes an algorithm package that delivers processed metrics on general activity classification, heart rate, heart rate variability, posture, sleep, and respiration during sleep.

2.1 Principles of Operation

When the facilitator configures the study design via the Web Portal, the study configuration is transferred to the Investigator Tablet App (and Link App for remote studies). The Investigator Tablet App and Link App are automatically configured for the specific study design, and when connected to Sensors, configure them per the study design. When user entered data including activity annotations and survey answers are sent from the Investigator Tablet App or Link App, the data travel to an MDDS storage system and are then accessible to facilitators via the Web Portal, which pulls the data from the MDDS storage system. Sensor data is transferred to the MDDS storage through the Link Hub and Link App. If the algorithm package was activated in the study, the algorithm module retrieves the data from the MDDS, processes the data and generates metrics that are returned to the MDDS system for storage. Study facilitators can access all study data (raw and processed) through the Web Portal.

2.2 Indications for Use

The BioStamp nPoint system is a wireless remote monitoring system intended for use by researchers and healthcare professionals for continuous collection of physiological data in home and healthcare settings. These physiological data include heart rate, heart rate variability, respiration rate, activity (including step count and activity classification), and posture (body position relative to gravity). The system is also intended for measurement of surface electromyography and to monitor limb or body movements during daily living and sleep. Data is transmitted wirelessly from the Sensors for storage and analysis.

The device is intended for use on general care patients who are 18 years of age or older as a general patient monitor to provide physiological information. The data from the BioStamp nPoint system are intended for use by researchers and healthcare professionals for research applications or, at the discretion of a qualified healthcare professional, as an aid to diagnosis and treatment. The device is not intended for use on critical care patients.

3.0 STUDY PURPOSE AND OBJECTIVES

The purpose of this pivotal study is to evaluate the performance, usability, and reliability of the BioStamp nPoint system for continuous collection of physiological data in remote (in-home) and healthcare (in-clinic) settings.

The primary objective of the clinical investigation is to evaluate the accuracy of the BioStamp nPoint system algorithm measurements and to evaluate the adhesion (reliability) of the Sensors.

Safety and tolerability will be further assessed via a follow-up telephone call.

4.0 STUDY ENDPOINTS

4.1 Effectiveness Endpoints

The effectiveness endpoints for this study are the various types of measurements made by the BioStamp nPoint system. All effectiveness endpoints to be statistically summarized will be collected using the BioStamp nPoint during in clinic supervised use. The effectiveness endpoints are as follows:

- Heart Rate (bpm)
- Heart Rate Variability (RMSSD³ (msec) and LF/HF Ratio⁴)
- Respiration (average respiration rate)
- Activity Classification (activities – sleep, standing, sitting, lying, walking and other)
- Activity Parameters - total step counts in a 6 minute walk test
- Sleep (sleep onset time (hours, minutes, and seconds), sleep wake time (hours, minutes, and seconds))
- Posture Classification (sleep posture, stationary posture standing, stationary posture sitting)

For each endpoint, the BioStamp nPoint measurements will be compared to a similar FDA-cleared measurement device, other measurement devices, or independent observer measurements. The FDA-cleared measurement devices used as comparators for this study are the Actiheart heart rate reference device and the Capnostream portable respiratory monitor.

Table 1 displays the comparator method for each endpoint category.

Table 1: Endpoint Variable Group and Measurement Comparator

| Index | Endpoint Variable Group | Measurement Comparator |
|-------|-------------------------|-----------------------------|
| 1 | Heart Rate | Actiheart Device |
| 2 | Heart Rate Variability | Actiheart Device |
| 3 | Respiration | Capnostream Device |
| 4 | Activity Classification | Independent Observer |
| 5 | Activity Parameters | Manual Step Counting Device |
| 6 | Sleep Parameters | Independent Observer |
| 7 | Posture | Independent Observer |

³ RMSSD: root-mean-square of successive difference of the time intervals between successive heartbeats.

⁴ LF/HF ratio: the ratio of power in the low-frequency (LF, 0.04-0.15 Hz) and high-frequency (HF, 0.15-0.4 Hz) bands of heart rate variability in the frequency domain.

Individual independent observers will receive training on the operation of all devices and execution of the study protocol before the enrollment of any subjects.

For heart rate and heart rate variability, the values collected will be the one minute average heart rate, the one minute RMSSD and the five-minute LF/HF ratio from the BioStamp nPoint and the one minute average heart rate, RMSSD and five minute LF/HF ratio from the Actiheart device on each of six recording times for each subject. Two readings will be taken while the subject is at rest, two while exercising and two while lying down.

For respiration rate, the average sleep respiration rate values will be collected at one minute time intervals during two separate nights of sleep on each subject using both the BioStamp nPoint and the Capnostream while the subject is asleep.

For the activity classification variable, each subject will be presented with five tasks (standing, sitting, lying, walking and stationary bike riding) in varied order and the activity classification will be recorded by the BioStamp nPoint and by the independent observer. This procedure will be repeated five times for each subject.

For the exercise parameter number of steps taken, the number of steps taken by the subject during a 6 minute walk test will be recorded using both the BioStamp nPoint and a simple step counting device.

For the sleep parameters sleep onset time and wake time, the BioStamp nPoint values and independent observer values will be collected on each night at the study site.

Posture classification variables will be analyzed separately for each type of posture activity (sleep positions, stationary posture standing and stationary posture sitting). For a given posture activity, the posture classification will be recorded by the BioStamp nPoint and the independent observer for two repeats each of each ground-truth posture for each subject. Since sleep position and lying posture are identical, this variable will be assessed from awake subjects to ensure that all postures are represented. Each repeat will generate 5 independent observations of posture. The posture classifications for each posture classification variable are given in Table 2.

Table 2: Posture Variable and Classification

| Index | Posture Variable | Posture Classification |
|-------|-----------------------------|---|
| 1 | Sleep positions | Supine, prone, left side and right side |
| 2 | Stationary Posture Standing | Upright, lean left, lean right, lean back, lean forward |
| 3 | Stationary Posture Sitting | Upright, lean left, lean right, lean back, lean forward |

In addition, sensor adhesion to the subject will be measured on a 4 point scale by the independent observer for each of four sensor patches on each subject following 24 hours of continuous wear. The adhesion rating scale (Table 3) is as follows:

Table 3: Sensor Adhesion Rating Scale

| Score | Rating | Description |
|-------|--|---|
| 0 | = ≥90% adhered | essentially no Sensor lift off the skin |
| 1 | = ≥75% to <90% adhered | some edges only of the Sensor lifting off the skin |
| 2 | = ≥50% to <75% adhered | less than half of the Sensor lifting off the skin |
| 3 | = >0% to <50% adhered but not detached | more than half of the Sensor lifting off the skin without falling off |
| 4 | = 0% adhered – Sensor detached | Sensor completely off the skin |

Usability will also be assessed by the clinician observing the subject using the system and via a subject questionnaire.

4.2 Safety

All adverse events (AEs) reported during the evaluation period will be collected and summarized. Serious AEs (SAEs) will be reported in accordance with US Code of Federal Regulation requirements.

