6.1 Study Duration

One supervised session of approximately four hours, with observation periods throughout and two night-time sleep periods; thus a total evaluation duration of approximately 48 hours.

At least one safety and tolerability follow-up call will occur within three to five days post-sensor removal.

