6.2 Schedule of Events

The evaluation period includes (refer to Section 4.1) clinician observed supervised testing. Subjects will wear a total of four BioStamp nPoint Sensors for this study; chest, thigh, shank, and forearm, and the BioStamp nPoint system will be configured, using only the chest and thigh Sensors, to measure and compute algorithm outputs.

In addition to the algorithm determinate Sensor locations, the shank and forearm Sensors (no sensor data will be collected) will be utilized in combination with the chest and thigh locations to validate the Sensor adhesion performance. The study is designed to capture supervised, observed measurements, as well as two nights of sleep in in clinic supervised setting.

Table 5: Schedule of Events

| Activities | Visit Day | Screening Period | Evaluation Period | | | | Safety Follow-Up |
|---|--------------|---------------------|-------------------|------------------|------------------|------------------|---------------------|
| | | 1 | Clinic 1 or 2 | Clinic 1 or 2 | Clinic 2 or 3 | Clinic 2 or 3 | Telephone |
| | | -60 to 0 | 0 | 1 | 1 | 2 | 3-5 |
| Screening & Enrollment Activities | | | | | | | |
| Informed Consent | | X | | | | | |
| Screening survey (demographics, medical history, etc.) | | X | | | | | |
| Baseline assessment (weight, Fitzpatrick, medical history, location irritation) | | X | X | | | | |
| Urine pregnancy and drug screen | | X | X | | | | |
| Sensor Application | | | | | | | |
| Application of Functional MC10 Sensors by Clinician | | | X | | | | |
| Application of Non-functional MC10 Sensors by Clinician | | | X | | | | |
| Adhesion application assessment | | | X | X | | | |
| Application of Functional MC10 Sensors by Subject | | | | X | | | |
| Application of Heart Rate Reference Device by clinician | | | X | | | | |
| Application of Respiration Reference Device for Sleep Respiration by clinician | | | X | | X | | |
| Prescribed Activities (Supervised) | | | | | | | |
| Activity Classification Activities | | | X | | | | |
| Heart Rate Activities | | | X | | | | |
| Subject training | | | | X | | | |
| Overnight sleep | | | X | | X | | |
| Prescribed Activities (Remote) | | | | | | | |
| | | | | X | | | |
| Time of Removal Assessments (MC10, Heart Rate Reference Device) | | | | | | | |
| Adhesion assessment | | | | X | | X | |
| Removal pain assessment | | | | X | | X | |
| Skin irritation assessment | | | | X | | X | |
| Sensor Removal | | | | | | | |

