| Removal of Respiration Reference Device for Sleep Respiration by clinician | | | | X | | X | |
| Removal of MC10 Sensors by clinician | | | | X | | | |
| Clean MC10 Sensors by clinician | | | | X | | | |
| Removal of MC10 Sensors by Subject | | | | | | X | |
| Clean MC10 Sensors by Subject | | | | | | X | |
| Removal of Heart Rate Reference Device by clinician | | | | | | X | |
| Usability Survey | | | | X | | X | |
| Data Transfer | | | | | | | |
| MC10 Sensor data transfer | | | | X | | X | |
| Respiration Reference Device data transfer | | | | X | | X | |
| Heart Rate Reference Device data transfer | | | | | | X | |
| Return sensors to investigators | | | | | | X | |
| Safety follow-up call | | | | | | | X |
| Recording of adverse events | | | X | X | X | X | X |

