8.12 Subject Follow-up

A Safety follow-up telephone call will be made between Day 3 and Day 5 to assess for adverse events associated with study participation.

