14.1.1 Adverse Events

Adverse events (AE) are any untoward medical occurrence, unintended disease or injury, or untoward clinical signs (including abnormal laboratory findings) in which subjects, users or other persons, whether or not related to the investigational medical device.

All adverse events, regardless of relationship to the device, must be recorded, as applicable, on the case report forms provided. Adverse events that occur during this study should be treated by established standards of care, which will protect the life and safety of the subjects.

Adverse events shall be assessed and documented at the time of the procedure and at all study follow-up visits. Each investigator shall provide source documentation as requested by the Sponsor to facilitate reporting and adjudication of these events.

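### The protocol contradicts itself on which adverse events count: Section 4.2 stops at the evaluation period, other sections run through the follow-up call, and Section 8.12 narrows what the call covers

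*Protocol*

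**What the plan says.** Section 4.2 (Safety) states: "All adverse events (AEs) reported during the evaluation period will be collected and summarized". The safety entry in the synopsis carries the same sentence.

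The evaluation period has a bounded meaning in this protocol. Table 5 (Section 6.2) places four clinic columns, Day 0 to Day 2, under that heading and puts the telephone contact in a separate safety follow-up column. Section 6.1 describes the supervised session and the two nights, "thus a total evaluation duration of approximately 48 hours", and mentions the call in its own paragraph.

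Other parts of the protocol reach further:

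- Section 3.0: "Safety and tolerability will be further assessed via a follow-up telephone call".
- Table 5: the row "Recording of adverse events" is marked in all four evaluation columns and in the follow-up column.
- Section 14.1 has AEs recorded for the whole study.
- Section 14.1.1: "All adverse events, regardless of relationship to the device, must be recorded, as applicable, on the case report forms provided". It also has AEs assessed at every follow-up visit.
- Section 11.6.3 summarises TEAEs by system organ class, preferred term and device relationship, and lists all AEs whether related or not. It sets no time window.

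Section 8.12 gives the purpose of the call as "to assess for adverse events associated with study participation".

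**The concern.** The safety endpoint statement and the rest of the protocol give different answers to a simple question: does an AE first mentioned on the follow-up call enter the AE summary? The call is the only contact that Table 5 schedules after the Day 2 visit. Skin reaction is the device effect anticipated in Section 14.5, which says that it can take a more severe form. Irritation is scored only at sensor removal (Sections 8.8.8 and 8.10.4), so a reaction that appears later can reach the record only through the call or a subject's own report. If Section 4.2 governs, such a reaction is recorded but left out of the summary that supports the 510(k) submission.

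The wording of Section 8.12 raises a second, separate problem. Relatedness is a graded judgement by the investigator (Section 14.3.3), with categories that include not related and unknown. A call that asks only about events linked to participation lets the caller or the subject make that judgement before anything is written down.

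**Working it through.** No statistical figure is involved. The check is a comparison of texts plus a day count.

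**Step 1. Is the call outside the evaluation period?** The last sensors come off on the morning of Day 2 (Section 8.10.3). The protocol gives two windows for the call:

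- Section 6.1 and the synopsis: three to five days after removal, so 2 + 3 = Day 5 to 2 + 5 = Day 7.
- Section 8.12: Day 3 to Day 5, so 3 − 2 = 1 to 5 − 2 = 3 days after removal.

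The two windows share only Day 5. The earliest possible call is Day 3, after the last evaluation column (Day 2), so the call lies outside the evaluation period under either window.

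**Step 2. Trace an AE first reported on the call.**

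| Place | Time limit stated | Treatment of an AE first reported on the call |
|---|---|---|
| 4.2 and synopsis | Evaluation period | Outside what is collected and summarised |
| 3.0 | None; the call is part of the safety assessment | Within scope |
| Table 5 | Follow-up column marked | Recorded |
| 14.1, 14.1.1 | Whole study, including follow-up visits | Recorded |
| 11.6.3 | None | Listed; summarised if it counts as a TEAE, a term the protocol does not define |

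Section 4.2 turns on when an event is reported. A reaction that began on Day 2 but was first mentioned on the call would therefore also fall outside it.

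**Step 3. What is not affected.** Irritation is scored immediately after removal on Day 1 (Section 8.8.8) and on Day 2 (Section 8.10.4). Both checks fall in evaluation columns. The subject stays in the clinic between them with AE recording continuing, so reactions seen at or between those checks are within Section 4.2.

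**Step 4. Section 8.12 against Section 14.1.1.** A delayed skin reaction to a sensor is linked to participation, so a call worded as in Section 8.12 would still elicit it. An event that the subject or caller presumes unrelated would not be asked about, although Section 14.1.1 requires it on the case report form. This conflict concerns presumed-unrelated AEs and is independent of the window in Section 4.2.

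**The case against.** The strongest reply is that Section 4.2 is a two-sentence endpoint summary and not the analysis rule. It does not say that later events are excluded. The analysis rule is Section 11.6.3, which has no evaluation-period limit and lists every AE. Table 5 and Sections 3.0, 14.1, 14.1.1 and 14.2 all point to collection over the whole study. A TEAE definition is normally left to the SAP, which is not shown.

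Much of this stands. Most of the text is on the inclusive side, nothing shows that the sponsor meant to exclude call-reported events, and the absent TEAE definition is not a fault in itself. But it does not remove the contradiction. Section 4.2 and the synopsis are the only places that attach a time window to the AE summary. A SAP author could read them together with Section 11.6.3, taking the window from the first and the table format from the second. Call-reported AEs would then be listed but not summarised. Reading Section 11.6.3 alone would include them. Both readings fit the text.

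Four stronger inferences are tempting and are not supported:

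- That late AEs are definitely lost and the AE rate is biased downward. This follows only if Section 4.2 is applied over the other sections.
- That every reaction found after sensor removal is left out. The Day 1 and Day 2 checks after removal are inside the evaluation period.
- That Section 8.12 would miss delayed skin reactions. Its wording covers them.
- That the share of calendar days falling after Day 2 measures the loss. Days are not events, and the protocol gives no AE rate or timing from which to derive one.

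**Conclusion.** The protocol contradicts itself in two places that should be reconciled. First, Section 4.2 and the synopsis limit the AE summary to reports made by Day 2, while Table 5 and Sections 3.0, 14.1, 14.1.1 and 11.6.3 either carry AE collection through the call or set no limit. Applied literally, Section 4.2 removes from the summary the AEs first reported after the Day 2 visit, and no others. Second, Section 8.12 gives the call a narrower scope than Section 14.1.1 allows, which could lose AEs presumed unrelated before they are graded.

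The size cannot be given as a number. Any effect on the reported AE count is downward if Section 4.2 or 8.12 is followed to the letter, and nil if the wider sections are followed. The conclusion rests on two readings: that the evaluation period means the Day 0 to Day 2 columns of Table 5, and that the link to participation in Section 8.12 is meant causally. It is a wording defect worth correcting, not evidence of a flawed safety design.

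**What to change.** - **Section 4.2 and the synopsis:** replace the limit to the evaluation period with a window that runs through the call, for example: AEs with onset from first application of any study device through the safety follow-up call will be collected and summarised.
- **Section 11.6.3:** refer to that same window for the AE summary, so that the SAP inherits one definition.
- **Section 8.12:** have the call ask about all adverse events whatever their presumed relationship, in line with Section 14.1.1, and leave relatedness to the grading in Section 14.3.3.
- **Call timing:** since the call would then close the window, the timing in Section 6.1 and the synopsis must be reconciled with that in Section 8.12.

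The cost is wording in these places and a revised call script, with no added visit or staff. The reported AE count may rise slightly.
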